11.4 Short-term Cost Analysis

We will compare mean direct medical costs, indirect (patient time) costs, total costs and quality-adjusted survival over the six-month follow-up period in the REHAB-HF intervention patients versus attention control. We will generate utility weights from the EQ-5D-5L collected data.

11.5 Long-term Cost-Effectiveness Analysis

We will also perform a cost-effectiveness analysis of the REHAB-HF intervention by combining estimated long-term costs and quality-adjusted survival with rehabilitation versus attention control. We plan to use our TEAM-HF Cost-Effectiveness Model(157) developed with NIH funding (R01 NR011873) to generate long-term estimates of costs, survival and quality-adjusted survival for patient-centered interventions in heart failure. We will conduct sensitivity analyses to evaluate the impact of varying the time horizon for the study and costs associated with the intervention.

11.6 Sustainability of the Intervention

To evaluate the sustainability of the intervention after the trial concludes, we will determine the extent to which the cost of the rehabilitation program is offset by savings from reductions in readmissions and other medical resources. This information will be used to propose payment models for 3rd party payers (e.g. CMS) and accountable care organizations and health maintenance organizations who provide care to heart failure patients on a capitated basis. If the intervention does not produce a net cost-savings, the cost-effectiveness analysis will assess

gains in health outcomes vs. incremental costs of the intervention, which will provide important information for coverage decisions.

12 Efficacy Parameters

12.1 Primary Efficacy Parameter

The primary outcome for assessing the efficacy of the REHAB-HF intervention will be change in physical function, as measured by the SPPB score, at 3 months.

12.2 Secondary Efficacy Parameter

The secondary outcome for assessing the efficacy of the REHAB-HF intervention will be the total number of all-cause rehospitalizations during the 6 months following discharge from the index hospitalization.

12.3 Exploratory Efficacy Parameters

The study will explore several other possible endpoints:

- 1. Change in the Kansas City Cardiomyopathy Questionnaire (KCCQ) total score and physical component score at 3 months
- 2. Change in 6-minute walk distance (6MWD) at 3 months
- 3. Change in component scores of the SPPB at 3 months
- 4. Change in the 12-item short form health survey (SF-12), depression, and cognition measures at 3 months
- 5. Change in frailty status at 3 months
- 6. All-cause rehospitalizations at 1 month and 3 months
- 7. All-cause rehospitalizations 6 months from the date of randomization
- 8. All-cause combined rehospitalization and death at 6 months
- 9. Global rank endpoint of SPPB score + all-cause rehospitalization + death
- 10. Heart failure (HF)-specific rehospitalizations
- 11. Cardiovascular events
- 12. All-cause rehospitalization days
- 13. Total hospitalization days post-randomization
- 14. Total facility-free days alive
- 15. Deaths
- 16. Falls
- 17. Change in biomarkers at 3 months

13. Safety Monitoring and Adverse Events

Safety Monitoring and Adverse Events, including falls, will be collected at all visits, recorded with clinical details on the case report form, discussed during the regular Operations Committee meetings (Section 16), and forwarded to institutional review boards and the data safety monitoring board (DSMB; see section 12.2). An independent DSMB, appointed by NIH and governed by NIH policy, will meet semi-annually (or more frequently as indicated) and will monitor study-wide safety and clinical events.

13.1 Adverse Events (AE) and Serious Adverse Events (SAE)

The following standard definitions of an adverse event and a serious adverse event are based on NHLBI policy as follows.

1. Adverse event (experience):

Any untoward medical occurrences in participants will be captured, regardless of causal relationship with the intervention and procedures. An AE can therefore be any unfavorable and

unintended sign (including an abnormal laboratory finding), symptoms, or disease temporally associated with the investigational intervention, whether or not considered related to the investigational intervention.

2. Serious adverse event (experience) (SAE):

Any untoward medical occurrences that may result in any of the following outcomes:

- Death
- Is life-threatening
- Requires inpatient hospitalization or prolongation of existing hospitalization
- Results in persistent or significant disability/incapacity
- Is a congenital anomaly/birth defect
- Important medical event that may not result in death, be life-threatening, or require
 hospitalization may be considered a serious adverse event when, based upon
 appropriate medical judgment, it may jeopardize the patient or participant and may
 require medical or surgical intervention to prevent one of the outcomes listed above

Disability is defined as a substantial disruption of a person's ability to conduct normal life's functions (Federal Code of Regulations 21 CFR 312.32)

For the purpose of the REHAB-HF study, the following AE's and SAE's will be reported to the DSMB: death, hospitalization, hospitalization/observation unit stay lasting less than 24 hours, emergency room visit, urgent clinic visits, and adverse events occurring while participant performing the REHAB-HF intervention (including angina, syncope/presyncope, palpitations, symptomatic hypoglycemia and/or falls). All cardiovascular events (including worsening heart failure, acute coronary syndrome, arrhythmia, and stroke) will be collected and reported to the DSMB. For the purpose of this protocol, hospitalizations will be identified as planned or not planned. We will not be collecting specific information on congenital anomalies. At the end of the study or at death, an attempt will be made to ascertain if any permanent disabilities occurred related to the intervention.

All SAE's will be coded using MedDRA. SAE's resulting in a death will be reported to the DSMB Chair and NIA program officer within 2 business days for deaths judged related in any way to the study and 5 business days if judged unrelated to the study. All serious adverse events will be reported by a blinded treatment arm ("A" and "B") to the DSMB Chair and the NIA Project Officer monthly.

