There will be 3 lead centers, Wake Forest Baptist Health, Duke University Medical Center, and Thomas Jefferson University and Hospital. Each lead center may recruit up to 3 geographically-close, tightly-affiliated 'satellite' sites under their direct management and budgetary control. Together, these sites will recruit a total of 360 consenting patients ≥ 60 years old hospitalized with ADHF. Following informed consent and baseline testing, the participants will be randomized in a 1:1 fashion to receive a 12-week novel, progressive, multi-domain rehabilitation and exercise training intervention or attention control. The multi-domain rehabilitation intervention will include endurance, mobility, strength, and balance training and will be tailored based on participant performance in each of these domains. It will begin upon randomization during the hospitalization and will continue 3 times per week in an outpatient setting. Participants randomized to the attention control arm will receive all services ordered by their primary physician and will be contacted bi-weekly by study staff. All participants will undergo measures of physical function and quality of life at baseline, 1 month, and 3 months. Clinical events will be monitored for 6 months following the index hospitalization.

By testing a novel rehabilitation intervention supported by multiple levels of evidence, this trial will address a critical evidence gap in the care of older patients with ADHF. The REHAB-HF results have the potential to shift paradigms by improving physical function and quality of life as well as clinical outcomes. If successful, the results could have a major impact on the management of patients with ADHF, the most common Medicare discharge diagnosis.

2. Study Objectives

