7.1 Attention Control

Participants randomized to the attention control arm will be notified immediately, and will follow standard care as ordered by their individual, treating physician. Importantly, to reduce the potential for bias from greater attention and surveillance in the rehabilitation intervention group, participants in the attention control group will receive at least bi-weekly contact from study personnel during the first 3 months following the index hospitalization. This contact will be provided as a combination of telephone calls and specified study visits. Specifically, contact will be made with study visits at weeks 4 and 12 and with telephone calls at weeks 2, 6, 8, and 10. Further, in-person contact will be made within the first 2 weeks following discharge for the purposes of retention (section 8.2.2). Consistent with the rehabilitation intervention group, telephone contact will also be made at weeks 14, 16, 20, and 24. Information regarding symptoms, HF transitional management program use, medical compliance, activity level, rehabilitation received, medical resource utilization, and clinical events will be collected at each of these encounters.

Participants in the attention control arm will not receive any specific rehabilitation recommendations or exercise prescription from study personnel. They may, however, receive any physical or occupational therapy deemed appropriate by their usual clinical care providers, both during the hospitalization and as outpatients.

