7.2.8 Exercise Safety

During each exercise session, participants will sign an attendance sheet and log any health-related problems or symptoms they are experiencing. These sheets will be reviewed by intervention staff before initiating physical activity. Should a participant report a significant change in health status (see safety parameters below) before or during exercise, a study physician onsite or the participant's primary doctor should be consulted prior to exercise participation. Vital signs, including heart rate, blood pressure and pulse oximetery will be recorded at the beginning and conclusion of each session. Routine assessment of heart rate during the exercise session will also be used to enhance exercise safety. Exercising blood pressure and pulse oximetery will be monitored on a symptom-driven basis as needed during the trial to ensure participant safety.

For participants who meet any of the safety parameters listed below, the following steps and additional monitoring procedures will be conducted:

- Exercise training sessions will be stopped
- The participant will subsequently be re-evaluated for medical contraindications to exercise
- Exercise intensity levels will be re-assessed and modified as needed

Safety Parameters

- Resting blood pressure systolic > 200 mm Hg or diastolic > 100 mm Hg
- Resting blood pressure systolic < 80 mm Hg
- Resting blood pressure systolic between 80 and 89 mm Hg with associated or uncertain symptoms of lightheadedness or dizziness

- Resting heart rate >120 beats/min or < 40 beats/min
- Increase in heart rate ≥90% of age predicted maximum during exercise
- Oxygen saturation < 90% on room air
- Unusual or severe shortness of breath
- Chest pain including chest discomfort or pressure, left arm pain, report of indigestion or stomach discomfort
- Palpitations
- Severe light headedness, dizziness or feeling about to faint
- A physical activity session had to be discontinued because of other symptoms excluding musculoskeletal symptoms (e.g. knees, ankles, hips) reported by the participant
- Decrease in diastolic blood pressure ≥20 mmHg during exercise
- Increase in systolic blood pressure to ≥250 mmHg or in diastolic blood pressure to ≥115 mmHg during exercise
- Decrease in oxygen saturation to <88% on room air during exercise

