10.6.2 Other Clinical Events

The study will also capture deaths, emergency department visits < 24 hrs, stays at observational units < 24 hrs, unscheduled, urgent medical visits, nursing home placement, myocardial infarction, stroke, serious arrhythmia, syncope, and falls. A fall will be defined as "an unexpected event in which the participants come to rest on the ground, floor, or lower level" as recommended by a recent consensus statement on defining falls as an outcome.(146)

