13.2 Data Safety Monitoring Board (DSMB)

An independent DSMB, appointed by NIH and governed by NIH policy, will be charged with monitoring study-wide safety and clinical events on a regular basis (semi-annually). In particular, the DSMB will review the following SAE's and the following specific clinical and safety events: death, hospitalization, hospitalization/observation unit stay lasting less than 24 hours, emergency room visit, urgent clinic visits, and adverse events occurring while participant performing the REHAB-HF intervention (including angina, syncope/presyncope, palpitations, symptomatic hypoglycemia and/or falls), cardiovascular events (including worsening heart failure, acute coronary syndrome, arrhythmia, and stroke), nursing home placement, and injury (or fall) during rehabilitation.

The protocol will guard against "unreasonable harm" by performing interim looks at DSMB meetings. The events included in this analysis will be death, disabling stroke, myocardial infarction, resuscitated sudden cardiac death, sustained symptomatic ventricular tachycardia, and ED visit or hospitalization for serious fall / injury.

14. Statistical Considerations

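### The DSMB lists in 13.1 and 13.2 include non-serious falls, syncope and minor symptoms only during the intervention, which is one-sided and conflicts with the section 13 introduction

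*Combined protocol and SAP*

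**What the plan says.** Section 13.1 names the events that go to the DSMB. Deaths, hospitalizations, short stays, emergency and urgent clinic visits, and all cardiovascular events are listed without regard to where they happen. One further item is limited to events during exercise: "adverse events occurring while participant performing the REHAB-HF intervention (including angina, syncope/presyncope, palpitations, symptomatic hypoglycemia and/or falls". Section 13.2 repeats it and adds "nursing home placement, and injury (or fall) during rehabilitation". The interim harm looks in 13.2 include serious falls or injuries leading to an emergency visit or admission, with no session limit.

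The introduction to section 13 is wider: "Safety Monitoring and Adverse Events, including falls, will be collected at all visits, recorded with clinical details on the case report form". It then says these are forwarded to the DSMB.

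Section 10.6 collects clinical events from randomization to 6 months after discharge, by interview at visits and calls and by records review. The events in 10.6.2 include "unscheduled, urgent medical visits, nursing home placement, myocardial infarction, stroke, serious arrhythmia, syncope, and falls", in either arm and in any setting. Falls are also an exploratory endpoint (12.3).

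On contact, 7.2.8 says that at each session "participants will sign an attendance sheet and log any health-related problems or symptoms they are experiencing". Section 7.1 says "participants in the attention control group will receive at least bi-weekly contact from study personnel during the first 3 months", and that symptoms and clinical events are asked about at each contact. Its stated purpose is to reduce bias from unequal surveillance.

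**The concern.** An event that must happen while someone performs the intervention cannot happen to a control participant. On that line the control count is zero by definition. The line can describe the safety of the sessions, but it cannot show whether the program raises or lowers falls overall. That question matters here. The protocol asks for close supervision to prevent falls (7.2.7.2, 7.2.7.4), prescribes home walking and strengthening on non-program days (7.2.9), and trains balance and strength, which might reduce falls.

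The documents also give two instructions. The section 13 introduction sends adverse events including falls to the DSMB, while the lists in 13.1 and 13.2 narrow this to falls during the intervention. Whoever prepares the DSMB report cannot tell which applies to a fall at home that needed no medical visit.

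A second issue concerns the data behind any by-arm table. If problems noted at sessions enter the event data, the intervention arm is observed far more often, and minor self-reported events may look more frequent there even when true rates are equal.

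**Working it through.** The plan states no figure on this point, so there is nothing to reproduce. The check compares the reporting routes and then counts contacts.

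**Routes to the DSMB under the lists in 13.1 and 13.2**

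| Event | Intervention arm | Control arm |
|---|---|---|
| Fall or syncope leading to an emergency, urgent clinic or hospital visit | Listed | Listed |
| Cardiovascular event, including acute coronary syndrome and arrhythmia | Listed | Listed |
| Fall or syncope without such a visit, during the intervention | Listed | Cannot occur |
| Fall or syncope without such a visit, at any other time | Not listed | Not listed |
| Presyncope, angina, palpitations or hypoglycemia without such a visit and not reported as a cardiovascular event | Listed only during the intervention | Not listed |

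The last three rows are the gap. For falls and syncope the two-arm data already exist under 10.6. For the minor symptoms in the last row they are less secure. Section 10.6.2 does not name those symptoms, so in controls they rest on the general adverse event definition in 13.1 and the symptom questions in 7.1.

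**Contacts through week 12**

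- Intervention sessions: 3 per week × 12 weeks = 36 (7.2.1). The completer threshold is 30 (7.3).
- Other intervention contacts: week 4 and week 12 visits, month 2 call and home visit = 4 (9.1, 7.2.9). Total 36 + 4 = 40.
- Control: 2 visits + 4 calls = 6, or 7 with the early in-person contact (7.1).

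Ratios:

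- 36/7 = 5.1 and 36/6 = 6.0 (planned sessions only)
- 30/7 = 4.3 and 30/6 = 5.0 (completer threshold)
- 40/7 = 5.7 and 40/6 = 6.7 (all intervention contacts)

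The range is 4.3 to 6.7.

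**Contacts over 6 months**

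Controls gain 4 calls, giving 10 or 11. The intervention arm gains 3 calls (months 4, 5 and 6 in 9.1) or 4 (if the week 14, 16, 20 and 24 calls in 7.1 apply to it). The extremes are (30 + 4 + 3)/11 = 37/11 = 3.4 and (36 + 4 + 4)/10 = 44/10 = 4.4.

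**The same count if session logs do not feed the event data**

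Counting only scheduled visits and calls by week 12, the intervention arm has 2 visits + 1 call = 3 and controls have 6. The imbalance then runs the other way.

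**What unequal detection could do**

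Allocation is "randomized in a 1:1 fashion", so equal true rates should give similar counts. If shares p_I and p_C of events are detected, the apparent rate ratio is p_I/p_C. The shares below are assumptions; the documents give none.

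- 1.0/0.9 = 1.11
- 0.9/0.7 = 1.29
- 0.9/0.5 = 1.80

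These show how a difference in detection carries through to the ratio. They do not estimate bias in this trial.

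**The case against.** The strongest reply is that the restricted line was never meant as an arm comparison. It covers the safety of the exercise sessions. Section 13.2 presents its list as particular items within a broader charge to monitor study-wide safety and clinical events, and the wider statement in the section 13 introduction may govern. This has force, but 13.1 introduces its own list as what will be reported, so the two instructions still need reconciling.

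A reader might infer that no valid comparison of falls or syncope between arms is possible. The documents do not support that. Both are collected in both arms by common methods to 6 months after discharge, falls have a written definition, and the consequential cases reach the DSMB without a session limit.

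A reader might also infer that the line unmasks the monthly A and B reports. Section 13.1 specifies masked-arm reporting for serious adverse events. It does not say that non-serious in-session events are tabulated that way.

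Nor is it shown that the comparison of falls is biased against the intervention. The log in 7.2.8 is reviewed before exercise begins and reads as a safety screen. The session data that 7.4 sends to the database are attendance and markers of adherence and progression. No section says that the log feeds the falls endpoint, although 10.6 and section 13 do not say whether a session counts as a visit. Events found through medical records also depend less on how often participants are asked. The possible bias therefore stands only as a conditional.

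Finally, restricting every comparison to contacts that both arms share could drop falls witnessed in sessions and events found in records. For a harm comparison that is the wrong direction in which to lose data, so the restriction belongs in a sensitivity analysis only.

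**Conclusion.** The point holds in a limited form. One item on the DSMB lists is one-sided by construction and conflicts with the introduction to section 13. The affected events are falls and syncope that lead to no emergency, urgent or hospital visit, and minor symptoms (presyncope, angina, palpitations, hypoglycemia). Serious falls and cardiovascular events are already covered in both arms, and the primary and secondary outcomes are not touched.

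The imbalance in observation is about 4 to 7 to 1 through week 12 and about 3.4 to 4.4 to 1 over 6 months. It matters only if session logs contribute to the event data. The count assumes attendance of 30 to 36 sessions and gives a session log the same weight as a call or visit. The size of any resulting bias cannot be derived from the documents.

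**What to change.** 1. Reconcile the section 13 introduction with 13.1 and 13.2, so that the DSMB receives, by masked arm, all falls and syncope collected under 10.6 in both arms, wherever they occur.
2. List in-session events separately as a subset. Because any such event belongs to the intervention arm, keep this listing apart from the A and B table, so that the new format does not itself reveal the arm.
3. State whether session logs feed the clinical event data, and record on the event form how each event was found: visit, call, records review or session.
4. Keep all events in the main safety comparison. Add a sensitivity comparison of falls limited to methods common to both arms: the 1- and 3-month visits, the calls at months 2, 4, 5 and 6, and records review.

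The cost is revised wording, one extra form field and one extra table. No new visits are needed, and falls and syncope are already collected.

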9.2 Blinding

The study will use a single-blind design where the study personnel assessing outcomes will be blinded to the study arm to which participants are assigned. To enhance continued blinding of assessors, participants will be asked not to disclose their assigned group during the assessment sessions.

10 Outcomes

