10.6 Clinical Measures

Clinical events will be collected prospectively from randomization until 6 months after discharge from the index hospitalization, the highest risk period for older ADHF patients, (44) by interviewing participants and family at each visit, phone calls, and medical records review.

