10.6.1 Rehospitalizations

All-cause rehospitalization was chosen as the secondary outcome because: 1) it is the most frequent adverse outcome in ADHF; 2) it is associated with impaired physical function, reduced quality of life, increased mortality, and increased cost; and 3) our pilot data and others' suggest that it is responsive to physical function interventions. A rehospitalization will be defined as a hospital stay > 24 hours, including prolonged emergency department visits or observational unit stays, for any cause and categorized according to the recommendations of Horwitz et al.(145) Rehospitalizations will be categorized by the site investigators as primarily due to non-cardiovascular, HF, or other cardiovascular (myocardial infarction, acute coronary syndrome without myocardial infarction, arrhythmia, peripheral vascular) cause, and whether they were related to the study intervention or assessments.

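### The only dedicated permanent-disability check in Section 13.1 looks for intervention-related cases alone, so it cannot give a figure for the control arm (minor safety-reporting point)

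*Combined protocol and SAP*

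**What the plan says.** Section 13.1 begins with a broad rule: "Any untoward medical occurrences in participants will be captured, regardless of causal relationship with the intervention and procedures". Its definition of a serious adverse event includes the criterion "Results in persistent or significant disability/incapacity", with no condition on cause. It then lists the events that go to the DSMB for this study, and disability is not on that list. Shortly after the list comes the only sentence that sets up a search for lasting disability, at the end of the study or at death: "an attempt will be made to ascertain if any permanent disabilities occurred related to the intervention".

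Relatedness is handled differently for two other serious outcomes. Under Section 10.6.1 all rehospitalizations count; site investigators classify each by cause "and whether they were related to the study intervention or assessments". Under Section 13.1 all deaths are reported, and relatedness changes only the deadline: "within 2 business days for deaths judged related in any way to the study and 5 business days if judged unrelated to the study".

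Other routes cover both arms. Section 13.1 states: "All serious adverse events will be reported by a blinded treatment arm". Section 10.6 gathers clinical events "by interviewing participants and family at each visit, phone calls, and medical records review". Section 13.2 has the DSMB review nursing home placement, and its interim harm looks include disabling stroke and serious fall or injury.

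**The concern.** In the disability sentence, relatedness decides whether a case is looked for at all. For rehospitalizations and deaths it is a label attached to an event already counted. Two consequences follow.

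First, the result rests on individual attribution. In a population that the Background describes as frail and multimorbid, with some patients never regaining baseline function, background disability is to be expected. It could be blamed on exercise, or a case caused by exercise could be put down to heart failure. Judging whether a disability is related to the rehabilitation in practice means knowing the arm. Section 9.2 blinds only one group: "the study personnel assessing outcomes will be blinded to the study arm to which participants are assigned". Section 13.1 does not say who makes the judgement.

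Second, there is nothing to compare the result with. Whatever number emerges for the intervention arm, the check cannot say whether permanent disability was more, equally or less common there than under control. For an exercise programme in frail older patients, that is a natural question for the DSMB and for readers.

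**Working it through.** The plan states no figure for permanent disability, so there is none to reproduce. The first step is textual.

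| Item | What is looked for or counted | Role of relatedness |
|---|---|---|
| Adverse events in general (13.1) | Any, whatever the cause | None at capture |
| Rehospitalization (10.6.1, 12.2) | Any cause | Recorded beside each event |
| Death (12.3, 13.1) | Any cause | Sets the reporting deadline |
| Permanent disability, dedicated check (13.1) | Intervention-related only | Filter on what is looked for |

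Section 7.1 gives control participants no rehabilitation advice or exercise prescription from study staff. A control participant therefore has no study rehabilitation to which a disability could be related, and the last row cannot produce a control case.

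The second step is whether another provision supplies the missing check. The serious-adverse-event criterion applies in both arms and is reported by masked arm, but it depends on someone reporting the disability; it is not a question put to everyone at the end. Disabling stroke, serious fall or injury, and nursing home placement cover particular pathways, not gradual loss of independence. In Table 2 the SPPB and SF-12 stop at 3 months, as does frailty in Section 12.3. The EQ-5D-5L is repeated at 6 months, and Section 10.2.3 uses its self-care item to flag need for help, but no comparison of that flag by arm is stated and it does not measure permanence.

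The third step is what an any-cause count in both arms could show.

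- Evaluable per arm: 360 / 2 = 180 randomized; 180 × 0.95 = 171, borrowing the 5% inevaluability allowance that Section 14.2 makes for rehospitalizations.
- Rate p of new permanent disability over 6 months: not in the documents; assumed 2%, 5% or 10% in both arms.
- Expected cases per arm, 171 × p: 3.4, 8.6 and 17.1.
- 95% confidence interval half-width for the difference, 1.96 × √(2p(1 − p)/171):
  - p = 2%: 1.96 × √(0.0392/171) = 3.0 points
  - p = 5%: 1.96 × √(0.0950/171) = 4.6 points
  - p = 10%: 1.96 × √(0.1800/171) = 6.4 points

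Such a count is useful as description and too imprecise to serve as a test.

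**The case against.** The strongest reply is that the general rule already does the work. Disability from any cause is a serious adverse event, and such events go to the DSMB Chair by masked arm each month. On this view the disputed sentence only adds a late search for treatment harm and removes nothing. Much of this stands. A reader might infer from the sentence that disability among control participants goes unrecorded; Sections 13.1 and 13.2 do not support that. What survives is that the general route is passive, that disability is absent from the study-specific DSMB list, and that the one active end-of-study search is one-sided.

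A second reply is that the protocol promises only to find out whether such cases occurred. It plans no tally and no comparison between arms. This also stands. A reader might go further and infer that the trial will publish a biased contrast, with some intervention cases set against none in control. The documents propose no such contrast, and its size would depend on assumed disability and attribution rates.

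A third reply is that rehospitalization is the secondary outcome and death an exploratory one, so all-cause counting is required for them, whereas disability is not an endpoint. That explains the different treatment, and I do not call it a contradiction. It does not make the narrower question the better one for safety.

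Finally, the remedy is weak as a test. At an assumed 5% control rate, a halving is a difference of 2.5 points. Its standard error is √((0.05 × 0.95 + 0.025 × 0.975)/171) = 0.0205, so z = 0.025/0.0205 = 1.22, and power is about Φ(1.22 − 1.96) = 23%. The wider question would not reliably separate no effect from a halving. This is correct, and it is why the count should be offered only as description.

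**Conclusion.** The point holds in a narrow form. Section 13.1's single dedicated check for permanent disability is limited to intervention-related cases, relies on attribution, and cannot give a control-arm figure. What the plan lacks is a systematic any-cause check in both arms; it does not lack every route by which control-arm disability could come to light. The textual finding needs no assumptions. The precision figures rest on assumed rates of 2 to 10% and 171 evaluable per arm.

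This is a minor safety-reporting matter, worth acting on because the change costs so little. The primary and secondary analyses, the sample size and the power are unaffected, and nothing in the documents supports treating it as a threat to the efficacy conclusions.

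**What to change.** In Section 13.1, reword the clause so that the attempt is to establish *if any new permanent disabilities occurred, in either arm and regardless of relation to the intervention*. Ask the question in identical words in both arms at the month-6 call that all participants already receive (Sections 7.2.11 and 9.1), or answer it from records when a participant has died. Record relatedness as a separate descriptor, as Section 10.6.1 does for rehospitalizations; this keeps the search for treatment harm. Report the count by arm to the DSMB and label it descriptive.

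The cost is one clause, one question and one line in the DSMB report, with no new visit, test or committee. There are three drawbacks. Precision is low, as shown above. Some disability in both arms will reflect progression of heart failure. The month-6 caller may know the arm, because Section 7.2.11 has intervention-arm calls also cover the exercise prescription; identical wording reduces that problem without removing it.
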